Project Title

Randomized, Controlled Study of Ultrasound-Guided Peripheral Venous Access Using AccuCath Versus Ultrasound-Guided Conventional Intravenous Catheter in the Emergency Department

Principal Investigators

[name] [name], MBA, MSc

Co-Investigators

[name], MBA, MS

Background & Significance

Peripheral venous cannulation is among the most common procedures performed in clinical settings and is a prerequisite for fluid resuscitation, administration of medications, and diagnostic testing^{1,2}. In the United States, approximately 300 million peripheral intravenous catheters (PIV) are inserted annually¹, and more than 25% of all visits to the emergency department require intravenous catheters for parenteral fluid administration³. Providers in the emergency department have become adept at establishing peripheral venous access, but it is estimated that PIV insertion fails for 6 million patients annually¹.

Many factors are thought to be associated with difficult venous access, which is typically defined to be at least two failed attempts at establishing intravenous access³. Intravenous drug abuse, obesity, multiple hospitalizations, and chronic medical problems including diabetes, sickle cell disease, end-stage renal disease, and cancer are predisposing factors for difficult venous access²⁻⁵. Prior studies have reported prevalence of difficult venous access ranging from 8% to 23%²⁻⁵. Failure to establish peripheral venous access in the emergency department is a costly problem, leading to delays in diagnostics and treatment and requiring alternative sites for vascular access such as external jugular, intraosseous, or central venous access³. These alternative methods can lead to higher complications rates, decrease patient satisfaction, and increase utilization of nursing and physician time⁶. Central venous catheterization, which is often used when traditional venous cannulation methods fail, has an overall complication rate of 15%, and complications include arterial puncture, pneumothorax, deep vein thrombosis, and infection^{7,8}. These complications pose a significant financial burden to the healthcare system, as the cost associated with a single central venous catheter related infection in 2002 was estimated to be \$34,508 to \$56,000 and the median payout for claims resulting from central venous catheter related injuries was \$100,750².

In the past few decades, ultrasound guidance has greatly improved the process of localizing vessels for cannulation, especially in patients with abnormal vascular anatomy or difficult venous access, thereby providing many benefits over landmark-based techniques. Ultrasound guided venous cannulation dates back to 1984, when Legler and Nugent showed that the single pass success rate for internal jugular (IJ) cannulation could be improved to 77.3% using Doppler ultrasound versus 28.6% for the traditional landmark-based approach⁹. Since the report of real-time ultrasonographic guidance of IJ catheter placement by Yonei et al. in 1986¹⁰, ultrasound guided central venous cannulation has repeatedly been shown to increase success rates, decrease complication rates, and improve patient satisfaction ^{1,2,11-15}. Based on the advantages offered by ultrasound guidance, the Agency for Healthcare Research and Quality now recommends real-time ultrasonographic guidance for all central venous access ^{13,16}.

The ultrasound-guided approach was adapted for peripheral venous access in the emergency department by Keyes et al. in an uncontrolled study that demonstrated a 91% success rate for ultrasound-guided cannulation of brachial and basilica veins¹⁷. A subsequent controlled study validated a higher success rate in the ultrasonographic (97%) versus control (33%) group in patients identified to have difficult PIV access and also showed that the ultrasonographic group required less time to successful cannulation, fewer percutaneous punctures, and resulted in greater patient satisfaction than the traditional landmark-based approach¹³. Furthermore, ultrasound-guidance for peripheral venous cannulation has been shown to prevent the need for central venous catheterization in 85% of patients with difficult venous access² and used 40% fewer kits per patient than landmark-guided placement of catheters^{11,18}. In a healthcare climate that is increasingly focused on outcomes and cost-effectiveness, ultrasound-guided peripheral venous cannulation has become not only a viable but often the preferred method in patients with difficult venous access.

Nevertheless, studies to date on ultrasound-guided peripheral venous cannulation have revealed some shortcomings. Conventional IV catheters placed under ultrasound guidance have been prone to premature failure with failure rates of 8% ^{7,17} in the first hours after placement and 47% in the first 24 hours, most commonly due to infiltration ⁷. These failure rates are significantly higher compared with 2% at 24 hours and 10% at day 4, which has been reported for standard peripheral IV catheters ^{7,19}. Moreover, while overall success rates range from 90% to 100% with multiple attempts ^{2,7,13,20}, first attempt success rate has been less impressive, ranging from 46% to 71% ^{13,20}. Our study will assess whether the AccuCath catheter with its integrated guidewire can address these shortcomings and demonstrate superiority over conventional PIV catheters across clinical outcomes relevant to the emergency department setting.

While catheters with guidewires have long been used when placing central and arterial lines, they have largely been absent from PIV placement. The AccuCath catheter is differentiated from conventional IV catheter in two principal ways. The catheter material consists of polyether block amide, which is a thermoplastic elastomer with softness and flexibility designed to decrease vessel wall irritation and mechanical phlebitis²¹. In addition, the integrated guidewire facilitates catheter insertion and limits vessel damage²¹. A prospective, randomized, controlled study has shown a first attempt success rate of 89% for AccuCath versus 47% for conventional IV along with lower complication rates of 8% for AccuCath and 52% for conventional IVs²¹. This study was performed in an inpatient setting on patients receiving elective, non-emergent PIVs²¹. Our study will be important in determining whether AccuCath's superior first attempt success rate and lower complication rate can be replicated in emergent PIVs in the emergency department setting. These improvements could translate to cost savings from decreased utilization of physician and nursing time, fewer number of PIV catheters used, higher patient satisfaction from fewer percutaneous punctures, and less complications from infiltration and phlebitis.

Purpose & Hypotheses

The objectives of the study are to:

1. In patients who fail traditional non-ultrasound IV catheter placement, compare ultrasound-guided cannulation of AccuCath catheters versus ultrasound-guided cannulation of conventional IV catheters in ED patients across the following clinical parameters: first attempt success rate, procedure time from the point of first percutaneous puncture to successful cannulation, total number of percutaneous punctures required for successful cannulation, and total number of IV

- catheters required for successful cannulation.
- 2. Assess patient and provider satisfaction with each catheter system on a 5-point Likert scale.
- 3. Check for clinical and demographic differences between patient groups that were successfully cannulated on first attempt versus those that required multiple attempts.

We hypothesize that:

- 1. Ultrasound-guided cannulation of AccuCath IV catheters will demonstrate a higher first attempt success rate, require less procedure time, require fewer percutaneous punctures, and utilize fewer catheters than ultrasound-guided cannulation of conventional IV catheters in ED patients.
- 2. Patients and providers will be more satisfied with AccuCath IV catheters versus conventional IV catheters in the ED setting.
- 3. There will be no statistically significant clinical and demographic differences between patient groups that are successfully cannulated on first attempt versus those that required multiple attempts.

Methods

I. Subject population (Patients)

- a. Inclusion criteria
 - English speaking patients, male or female, aged ≥18 years presenting to the UCMC Mitchell ED with Emergency Severity Index (ESI) from 1 to 5 anytime during Monday through Sunday.
 - Capable and willing to provide informed consent
 - Acceptable candidate for ultrasound-guided PIV per Mitchell ED protocol (i.e. 3 failed attempts by nurses- 2 by primary nurse, 1 by senior nurse)

b. Exclusion criteria

- Lack of decisional capacity (e.g., intoxication, dementia, delirium, developmental delay)
- Prior venous grafts or surgery at target IV site

II. Subject population (Providers)

UCMC emergency faculty and resident physicians.

III. Study implementation

1. Provider consent

We will obtain oral consent from UCMC emergency faculty and resident physicians, and nurses who have previously undergone ultrasound-guided PIV training, scheduled to work in the Mitchell Emergency Department during the study period. Typically, providers will be consented for participation in the study as group during academic conference hours or during ultrasound-guided PIV training sessions for nurses.

2. Patient recruitment and IV placement

We will use an unbiased mechanism for identifying a random cohort of ED patients. We will generate a randomization schedule for two treatment groups using 25 blocks of 20 patients. We expect to enroll a total of 500 patients in our study, 250 patients in each treatment arm.

A written patient consent form will explain that patients will be randomized to receive either ultrasound-guided cannulation of an AccuCath catheter (Group A) or ultrasound-guided cannulation of a

conventional IV catheter (Group B). The consent form will also explain that anonymized records of their clinical and demographic information will be used for research purposes. Patients will be able to refuse to participate in our study.

If a patient agrees to participate in the study, he or she will undergo either ultrasound-guided cannulation of an AccuCath catheter or ultrasound-guided cannulation of a conventional PIV catheter, both of which are currently used in clinical practice. Following ultrasound-guided IV cannulation, patients will be asked to respond to survey questions that will assess patient satisfaction with the IV catheter received and will document past history of IV drug use, smoking, dialysis, difficult IV stick, diabetes, sickle cell disease, cancer chemotherapy, hypertension, and congestive heart failure.

3. Provider's assessment

Providers will be required to complete a standardized form documenting the ultrasound-guided IV cannulation procedure. The form will ask for: laterality of IV site, number of percutaneous punctures, procedure time, number of IV's used, overall satisfaction with IV catheter.

4. Data acquisition

All patients admitted to the ED at UC are identified using hospital and physician records, including patient age, gender, and race. Relevant demographic data along with emergency severity index, body mass index, blood pressure, and past history of IV drug use, smoking, dialysis, difficult IV stick, diabetes, sickle cell disease, cancer chemotherapy, hypertension, and congestive heart failure will be collected from the patients or extracted from EPIC and used to understand the demographic and clinical characteristics of our study participants, with PHI exclusions. The analysis of the data will help us understand the generalizability of our findings based on the characteristics of our study population.

Protocol Duration

2 years

Research Location(s)

UCMC (Mitchell Hospital, Emergency Department)

Special Precautions

Special precautions will be taken throughout the data collection process, including:

1. Performance results of AccuCath vs conventional IV catheters

In order to avoid influencing care decisions, all clinicians and patients will be blinded to aggregate performance results comparing AccuCath IV versus conventional IV catheters. Only study personnel will have access to aggregate results comparing AccuCath IV with conventional IV catheters.

2. MRN and Study ID

The study ID will be linked to the MRN in a password-protected database. No one besides the specified study personnel will have access to the records or data.

3. Clinical Data

Clinical data will be entered directly to a password-protected database. No one besides the specified study personnel will have access to the records or data.

4. Satisfaction survey data

Patient satisfaction survey data will be entered directly to a password-protected database. No one besides the specified study personnel will have access to the records or data.

5. Provider's assessment data

Providers will indicate their assessment of catheter performance on a form that will be collected and accessed only by the study personnel. The data will be transferred to a password-protected database, and the physical copies will be destroyed as soon as data transfer is completed.

Statistical Analysis

Our primary outcome will compare the first attempt success rate of ultrasound-guided AccuCath IV cannulation versus that of ultrasound-guided conventional IV cannulation in ED patients. Our sample size of 250 patients for each treatment group has been 80% powered to detect a difference of 10% (2-sided, α =0.05). Our secondary outcome measures include procedure time from the point of first percutaneous puncture to successful cannulation, total number of percutaneous punctures, total number of IV catheters used, and patient satisfaction.

We will also check for clinical and demographic differences that may have contributed to difficult venous access.

Potential Benefits and Risks to Subjects

The risks associated with the use of our experimental catheter are comparable to the anticipated risks of standard IV therapy, which include infection, infiltration, extravasation, phlebitis, dislodgement, bleeding, hematoma, and pain at IV site. There is possibility that the experimental catheter's guidewire could cause intimal damage, but the guidewire has been designed specifically to minimize this risk, which is shared by conventional IV catheters.

References

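### Hypothesis 3 predicts non-significance, so failing to reject would count as support although no margin or interval is given

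*Combined protocol and SAP*

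**What the plan says.** All references are to the combined protocol and SAP.

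- Purpose & Hypotheses, hypothesis 3: "There will be no statistically significant clinical and demographic differences between patient groups that are successfully cannulated on first attempt", compared with those who needed more than one attempt.
- Purpose & Hypotheses, objective 3, is phrased neutrally: "Check for clinical and demographic differences between patient groups that were successfully cannulated on first attempt versus those that required multiple attempts".
- Statistical Analysis gives this aim one sentence: "We will also check for clinical and demographic differences that may have contributed to difficult venous access". It names no test, model, margin, interval or rule for multiple comparisons.
- The only significance level and power statement is in Statistical Analysis: 250 patients per group "has been 80% powered to detect a difference of 10" percent, 2-sided at 0.05. It belongs to the primary comparison of first-attempt success between arms.
- Methods III.4 (Data acquisition) lists what is collected. One part of the list reads: "body mass index, blood pressure, and past history of IV drug use, smoking, dialysis, difficult IV stick, diabetes, sickle cell disease, cancer chemotherapy". The other items are age, gender, race, the severity index, heart failure and hypertension. That is 15 characteristics, nine of them history items.

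**The concern.** Objective 3 asks whether patients with first-attempt success differ from the rest. Hypothesis 3 answers in advance that no difference will reach significance. Read literally, the hypothesis is supported whenever the tests fail to reject, and nothing in the plan says how small a difference must be to count as none. A non-significant result can mean that the groups are alike, or that 500 patients split into two unequal groups could not tell.

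The wording also exposes the hypothesis to the opposite error. It covers a whole set of characteristics, so a single chance p<0.05 would contradict it even if nothing truly differed.

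At stake is the reading of a third-ranked aim. Methods III.4 says the patient characteristics will inform generalizability, so a statement that nothing differed could be carried into that discussion.

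**Working it through.** **The plan's own figure.** There is none for hypothesis 3. The 250 per arm and the 10-point difference concern the primary comparison, so there is nothing to reproduce for this aim.

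**Inputs from the plan.** 500 patients (Methods III.2); 15 characteristics (Methods III.4); 2-sided 0.05, stated only for the primary comparison and borrowed here. Background & Significance gives first-attempt success of 46% to 71% in earlier ultrasound-guided studies, and 89% vs 47% in the earlier inpatient trial of the device.

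**Assumptions.** Yes/no characteristics with illustrative prevalences of 10% to 30% in the success group. Overall success and the resulting split (success / other):

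- 46%: 230/270 (low end of the earlier range, no arm difference)
- 51%: 255/245 (46% and 56%)
- 68%: 340/160 (47% and 89%)
- 76%: 380/120 (71% and 81%)
- 80%: 400/100 (71% and 89%, figures from different studies)

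**Step 1: power for one characteristic.** Two-proportion z-test with pooled null variance:

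Power = Φ[(d − 1.96·SE0)/SE1] + Φ[(−d − 1.96·SE0)/SE1], where SE0 = √[p̄(1−p̄)(1/n1+1/n2)] and SE1 = √[p1(1−p1)/n1 + p2(1−p2)/n2].

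Example, 340/160 and 20% vs 25%: p̄ = (68+40)/500 = 0.216; SE0 = 0.0395; SE1 = 0.0405. Power = Φ[(0.05 − 0.0773)/0.0405] + a second tail of 0.0008 = 0.251.

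| Success vs other | 230/270 | 255/245 | 340/160 | 380/120 | 400/100 |
|---|---|---|---|---|---|
| 10% vs 15% | 0.386 | 0.395 | 0.378 | 0.342 | 0.317 |
| 20% vs 25% | 0.263 | 0.268 | 0.251 | 0.225 | 0.207 |
| 30% vs 40% | 0.646 | 0.651 | 0.599 | 0.531 | 0.484 |
| 10% vs 20% | 0.878 | 0.882 | 0.847 | 0.793 | 0.750 |

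The two 5-point rows span 21% to 40%. A 5-point difference from 30% does worse, at about 17% to 22%.

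**Step 2: what a null estimate leaves open.** 95% CI half-width at zero observed difference = 1.96·√[p(1−p)(1/n1+1/n2)]. Example, 340/160 at 20%: 1.96·√(0.16 × 0.00919) = 7.5 points. Across the splits it is 5.3 to 6.6 points at 10% prevalence, 7.0 to 8.8 at 20% and 8.0 to 10.0 at 30%.

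**Step 3: the hypothesis as a whole, with 15 separate tests at 0.05.**

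- Nothing truly differs: P(at least one p<0.05) = 1 − 0.95^15 = 0.537. With all test statistics correlated at 0.3 it is 0.457.
- One true 5-point difference: P(all 15 non-significant) = (1 − power) × 0.95^14. This runs from 0.605 × 0.488 = 0.295 to 0.793 × 0.488 = 0.387, or 0.344 to 0.456 at correlation 0.3.
- Five true differences of 20% vs 30%: at worst (1 − 0.573)^5 × 0.95^10 = 0.0142 × 0.599 = 0.0085. At correlation 0.3 it stays below 0.03.

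Under independence, then, the prediction comes true in 46% of trials when nothing differs (1 − 0.537) and in 30% to 39% when one characteristic differs by 5 points. The outcome barely separates the two situations. It does separate them from five 10-point differences.

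**The case against.** The strongest reply is that this reads a decision rule into a one-line prediction. Objective 3 and the Statistical Analysis section speak only of checking, and the aim sits outside the listed primary and secondary outcomes. No section says that p>0.05 will be reported as proof that patient characteristics do not matter. A reader might infer that intention, but the documents do not state it; it is only a risk that the wording leaves open. What stands is that hypothesis 3 is one of three numbered hypotheses, is not labelled exploratory, and is met by failing to reject.

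The figures are also illustrative. The plan does not say that all 15 items will be tested separately, or at 0.05. Age, body mass index and blood pressure are usually continuous, race and severity index have several levels, and the prevalences are assumed. This is fair, and the results are given as ranges for that reason.

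Three stronger readings should be resisted.

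- Background & Significance states: "Intravenous drug abuse, obesity, multiple hospitalizations, and chronic medical problems including diabetes, sickle cell disease, end-stage renal disease, and cancer are predisposing factors". A reader might conclude that true differences are to be expected. That list concerns difficult access, and everyone enrolled has already had "3 failed attempts by nurses". The documents do not say that the same factors predict first-attempt failure under ultrasound.
- The Statistical Analysis sentence refers to difficult venous access and not to first-attempt success. This is better read as loose wording for objective 3 than as a second, conflicting analysis, and the point does not depend on it.
- Patients who are never cannulated have no obvious place in objective 3's two groups. That is a separate question of definition, not needed here.

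**Conclusion.** The point holds as a minor one. Hypothesis 3 makes non-significance its criterion without a margin or interval, and for modest differences that criterion fails both ways: it can easily be met when a 5-point difference exists, and it is contradicted by chance in roughly half of trials when none does. This rests on the assumed prevalences and success rates, yes/no characteristics, a borrowed 0.05 level and, for the joint figures, 15 separate tests.

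The size is limited. A reader might infer from the low single-characteristic power that a broad false all-clear is likely. It is not: several differences of 10 points would rarely all be missed. The randomised primary comparison does not depend on this aim.

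**What to change.** 1. Restate hypothesis 3 as an exploratory estimation aim.
2. For each characteristic in Methods III.4, report the difference in proportions or means between the two groups named in objective 3, with a 95% CI. Label these results exploratory and unadjusted for multiplicity.
3. State that no conclusion of no difference will be drawn from p>0.05.

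The cost is rewording, slightly longer reporting and no new data. The downside is that, if nothing truly differs, about 15 × 0.05 = 0.75 of the 15 intervals are expected to exclude the null by chance, which is why the exploratory label is needed.

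### History of difficult IV stick is asked after the ultrasound-guided cannulation, so answers to this one item in the objective 3 comparison may be coloured by the result that defines the groups (minor)

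*Combined protocol and SAP*

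**What the plan says.** **Timing.** Methods III.2 places the patient survey after the procedure: "Following ultrasound-guided IV cannulation, patients will be asked to respond to survey questions". Besides satisfaction, the same survey "will document past history of IV drug use, smoking, dialysis, difficult IV stick" and five further conditions, nine history items in all.

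**Source.** Methods III.4 (Data acquisition) lists the same history items and says that they "will be collected from the patients or extracted from EPIC". It does not say which source applies to which item, which takes precedence, or that an EPIC entry must predate the visit.

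**Use.** Objective 3 under Purpose & Hypotheses is to "Check for clinical and demographic differences between patient groups that were successfully cannulated on first attempt versus those that required multiple attempts". Hypothesis 3 predicts: "There will be no statistically significant clinical and demographic differences between patient groups that are successfully cannulated on first attempt" compared with those needing more. The Statistical Analysis section gives this comparison one sentence, outside the primary and secondary outcomes.

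**Eligibility.** The inclusion criteria (Methods I.a) require "3 failed attempts by nurses- 2 by primary nurse, 1 by senior nurse". The Background refers to "difficult venous access, which is typically defined to be at least two failed attempts at establishing intravenous access". The survey item itself is not defined.

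**The concern.** Most of the history items are conditions that today's punctures cannot change. A history of difficult sticks is different: it asks for a judgement about the same kind of event that the patient has just been through. Two things can go wrong.

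1. **Outcome-dependent answers.** A patient who has just needed several ultrasound-guided punctures may be readier to report earlier difficulty than one cannulated at the first try. Objective 3 groups patients by exactly that result, so the item could look like a predictor when it is partly a consequence.
2. **Counting today's sticks.** All participants arrive with three failed nurse attempts. If some patients in both groups report these as history, the groups become more alike on the item. A real difference shrinks, which favours the prediction of no difference in hypothesis 3.

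The two effects pull in opposite directions. At stake is how this single item is read. Previous difficulty is nevertheless an obvious candidate among factors that may explain difficult access, which the Statistical Analysis section says will be examined.

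**Working it through.** The plan gives no figure on this point, so there is nothing of its own to reproduce. The check is first one of sequence, then an illustration with assumed inputs.

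**Sequence of events**
1. Three failed nurse attempts (Methods I.a): common to all participants.
2. Ultrasound-guided cannulation: the first attempt succeeds or does not. This fixes the objective 3 group.
3. Survey, including the difficult-stick item (Methods III.2).
4. Comparison of the item between the groups fixed at step 2 (objective 3, hypothesis 3).

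The answer at step 3 follows the grouping at step 2. By then a first-attempt success has had at least 3 + 1 = 4 attempts that day, and a multiple-attempt patient at least 3 + 2 = 5. The three nurse attempts can only dilute; only the ultrasound-guided attempts differ between groups.

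**Illustration: inputs**
- From the documents: 500 patients (Methods III.2).
- Assumed: first-attempt success of 50–80% overall, giving splits of 250:250, 300:200, 350:150 and 400:100. The Background loosely anchors this with 46–71% for earlier ultrasound-guided placement and 89% versus 47% in the earlier randomised comparison.
- Assumed, with no anchor in the documents: prevalence of reported history, the reporting gap, the share counting today, and a true difference of 15 points.

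Formula: two-sided pooled two-proportion z-test at 5%. With reported proportions a and b in groups of n₁ and n₂, d = b − a and pooled proportion p̄:
- SE₀ = √[p̄(1−p̄)(1/n₁+1/n₂)]
- SE₁ = √[a(1−a)/n₁ + b(1−b)/n₂]
- P(significant) = Φ[(d − 1.96·SE₀)/SE₁] + Φ[(−d − 1.96·SE₀)/SE₁]

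**(a) Over-reporting only in the multiple-attempt group, no true difference.** Example: 300:200, reported 60% versus 65%. Then p̄ = (180 + 130)/500 = 0.62, SE₀ = 0.0443, SE₁ = 0.0440, and (0.05 − 0.0868)/0.0440 = −0.84, so the probability is about 20%. Over all four splits and prevalences of 40–70%:

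| Reporting gap | Chance of a false significant result |
|---|---|
| 0 points | 5% |
| 2 points | 6–8% |
| 3 points | 8–12% |
| 5 points | 14–24% |

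With equal true prevalence, over-reporting that is equal in both groups leaves the rate at 5%.

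**(b) Today's sticks counted equally in both groups.** If a share s of those without earlier history answer yes, the reported proportion is p + s(1−p), and a true difference of 0.15 becomes 0.15(1−s). Example: 300:200, true 50% versus 65%. The ranges cover all four splits and 40%, 50% or 55% in the first-attempt group.

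| s | Reported proportions (example) | Difference | Power (example) | Power (range) |
|---|---|---|---|---|
| 0 | 50% vs 65% | 15 points | 92% | 77–94% |
| 0.2 | 60% vs 72% | 12 points | 79% | 58–84% |
| 0.4 | 70% vs 79% | 9 points | 61% | 39–67% |

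**Hypothesis 3 as a whole.** Age, gender, race, severity index, body mass index and blood pressure plus nine history items make 15 characteristics. If all were independent with no true difference, the chance of at least one p < 0.05 is 1 − 0.95¹⁵ = 54%. Raising this one item from 5% to 10% gives 1 − 0.95¹⁴ × 0.90 = 56%.

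**The case against.** The strongest case on the other side has four parts.

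- **Past history ordinarily means before the present encounter**, and the item stands beside conditions such as diabetes and dialysis. This stands in part. The plan leaves the index visit unaddressed; it does not include it. The questionnaire is not in the documents, so its final wording cannot be checked. Even a patient who excludes today's sticks, however, answers a subjective question after knowing the result.
- **The contrast in experience is narrow**: at least four attempts versus at least five, not easy versus difficult. This stands. Illustration (a) puts all over-reporting in one group, which is the case least favourable to the plan.
- **EPIC is already a permitted source, and study IDs are linked to record numbers** ("The study ID will be linked to the MRN in a password-protected database", Special Precautions item 2), so earlier entries could be sought later. This mitigates the problem but does not settle it: the plan does not require EPIC for this item, and the documents do not say whether EPIC holds it.
- **The consequence is small.** This stands and sets the severity.

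A reader might go further and infer that every participant will answer yes, because all meet the Background's description of difficult access on the day. The documents do not support that. The Background reports a typical definition of difficult venous access; it does not define the survey item, and meeting it today does not show that patients will report today as history.

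**Conclusion.** The point holds, at minor severity. The stated timing lets the result of the first ultrasound-guided attempt influence a subjective item that is then compared between groups defined by that result. Counting of today's nurse attempts is a possible second distortion, in the opposite direction. The net direction is unknown, and the size cannot be computed: the documents give neither a prevalence nor a reporting gap. The illustrations show only what would follow from assumed values and should not be read as estimates.

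The harm is limited to one item of a descriptive objective. Two wider readings are not supported. A reader might infer that all the post-procedure history items are compromised; nothing in the documents suggests that answers on the other eight would change with the cannulation result. A reader might also infer that hypothesis 3 as a whole, or the trial's main result, is undermined. The move from 54% to 56% shows how little one item adds to the first, and the randomised comparison of first-attempt success does not use this item.

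**What to change.** - Ask this one item before the first ultrasound-guided puncture, for example at the consent contact, or take it from EPIC entries dated before the index visit. What matters is that it precedes the procedure, since objective 3 groups by the procedure's result and not by allocated arm.
- Word it as difficult IV access at visits before today. This is needed even at consent, which can follow the three nurse attempts.
- Record the source and timing of each answer.
- Where only a post-procedure answer exists, keep it, flag it, and show the comparison of this item with and without such answers.

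The other history items need not move. The cost is one short question before the procedure, one change of wording and a source-and-timing field, with possibly a few missing values in urgent patients.
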